3.9.2. Clinical Laboratory Parameters

Laboratory parameters will be presented in conventional (ie, US) units. Only scheduled laboratory parameters will be included in the summaries, unless specified otherwise. All laboratory data, including those collected at unscheduled visits, will be included in the listings.

Laboratory results including baseline and change from baseline for the Safety Population during the treatment period for chemistry and hematology parameters will be summarized by treatment sequence, overall, and by visit.

Clinical laboratory test values, scheduled or unscheduled, will be considered potentially clinically significant (PCS) if they meet PCS criteria listed in [Table 1](#). The number and percentage of subjects who have postbaseline PCS clinical laboratory values will be summarized by treatment sequence and overall. The percentages will be calculated based on the number of subjects with non-PCS baseline value and have at least 1 postbaseline assessment. All PCS values including baseline PCS values will be included in supportive listings.

Shift tables for selected metabolic parameters (glucose, total cholesterol, LDL, HDL, tryglyceride, and HbA1c) and liver function tests will be presented. The criteria are summarized in [Table 2](#), [Table 3](#) and [Table 4](#).

Table 1: Criteria of Potentially Clinically Significant (PCS) Abnormality for Selected Analytes

Parameters	Criteria
Chemistry	
Albumin	<2.5 g/dL
Alkaline Phosphatase (U/L)	$\geq 3 \times \text{ULN}$
Alanine Aminotransferase (U/L)	$\geq 3 \times \text{ULN}$
Aspartate Aminotransferase (U/L)	$\geq 3 \times \text{ULN}$
Bilirubin, Total	$\geq 2.0 \text{ mg/dL}$
Blood Urea Nitrogen	$>30 \text{ mg/dL}$
Cholesterol, Random	$>300 \text{ mg/dL}$
Cholesterol, Fasting	$\geq 240 \text{ mg/dL}$
Cholesterol, HDL Fasting	$\leq 30 \text{ mg/dL}$
Cholesterol, LDL Fasting	$\geq 160 \text{ mg/dL}$
Creatine Kinase (U/L)	$\geq 3 \times \text{ULN}$
Creatinine	$\geq 2.0 \text{ mg/dL}$
Glucose, Random	$<50 \text{ mg/dL}$ or $\geq 200 \text{ mg/dL}$
Glucose, Fasting	$<50 \text{ mg/dL}$ or $\geq 126 \text{ mg/dL}$
Potassium	$<3 \text{ mmol/L}$ or $>5.5 \text{ mmol/L}$
Lactate Dehydrogenase (U/L)	$>3 \times \text{ULN}$
Prolactin (Female)	$>30 \text{ ng/mL}$
Prolactin (Male)	$>20 \text{ ng/mL}$
Sodium	$<130 \text{ mmol/L}$ or $>150 \text{ mmol/L}$
Triglycerides, Fasting (Female)	$\geq 120 \text{ mg/dL}$
Triglycerides, Fasting (Male)	$\geq 160 \text{ mg/dL}$

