Table 1: Criteria of Potentially Clinically Significant (PCS) Abnormality for Selected Analytes (Continued)

Parameters	Criteria
Hematology	
Eosinophils	$>1.0 \times 10^3/\mu\text{L}$
Hematocrit (Female)	$\leq 32\%$
Hematocrit (Male)	$\leq 37\%$
Neutrophils, Absolute	$<1.5 \times 10^3/\mu\text{L}$
Platelets	$<75.0 \times 10^3 \text{ cells}/\mu\text{L}$ or $\geq 700.0 \times 10^3 \text{ cells}/\mu\text{L}$
Leukocytes	$\leq 2.8 \times 10^3/\mu\text{L}$ or $\geq 16.0 \times 10^3/\mu\text{L}$

Table 2: Shifts Category from Baseline to Any Postbaseline for Selected Lipid Parameters

Total cholesterol (fasting) mg/dL
Normal (<200) to High (≥ 240)
Borderline (≥ 200 and < 240) to High (≥ 240)
Normal/Borderline (<240) to High (≥ 240)
Normal (<200) to borderline/High (≥ 200)
Increase ≥ 40 mg/dL
LDL Cholesterol (fasting) mg/dL
Normal (<100) to high (≥ 160)
Borderline (≥ 100 and <160) to high (≥ 160)
Normal/borderline (<160) to high (≥ 160)
Normal (<100) to borderline/high (≥ 100)
Increase ≥ 30 mg/dL
HDL Cholesterol (fasting) mg/dL
Normal (≥ 40) to low (<40)
Decrease ≥ 20 mg/dL
Triglycerides (fasting) mg/dL

Normal (<150) to high (≥200)
Normal (<150) to very high (≥500)
Borderline (≥150 and <200) to high (≥200)
Borderline (≥150 and <200) to very high (≥500)
Normal/borderline (<200) to high (≥200)
Normal/borderline (<200) to very high (≥500)
Normal (<150) to borderline/high/very high (≥150)
Increase ≥50 mg/dL

Table 3: Shift Category from Baseline to Any Postbaseline in Glucose and HbA1c

Serum glucose (fasting) mg/dL
Normal (<100) to High (≥126)
Impaired (≥100 and <126) to High (≥126)
Normal/Impaired (<126) to High (≥126)
Increase ≥10 mg/dL
HbA1c %
Shift from baseline (<5.7%) to postbaseline ≥5.7%
Shift from baseline (<5.7%) to postbaseline ≥5.7% and <6.5%
Shift from baseline (<5.7%) to postbaseline ≥6.5%

Table 4: Shift Category from Baseline to Any Postbaseline in Liver Function Test

Alanine Aminotransferase (ALT) (U/L)
Shift from Normal to ≥3 x ULN
Shift from Normal to ≥5 x ULN
Shift from Normal to ≥10 x ULN
Aspartate Aminotransferase (AST) (U/L)
Shift from Normal to ≥3 x ULN
Shift from Normal to ≥5 x ULN
Shift from Normal to ≥10 x ULN
Bilirubin, Total (mg/dL)

Shift from Normal to >1 x ULN
Shift from Normal to ≥ 2 x ULN

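### The only table that grades ALT and AST rises by severity counts subjects with a normal baseline only, so severe rises from a raised baseline are not tabulated by grade.

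*SAP*

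**What the plan says.** SAP 3.9.2 plans shift tables for selected metabolic parameters and liver tests. The liver table is "Table 4: Shift Category from Baseline to Any Postbaseline in Liver Function Test". For both ALT and AST it has three rows: "Shift from Normal to ≥3 x ULN", "Shift from Normal to ≥5 x ULN" and "Shift from Normal to ≥10 x ULN". Bilirubin also has only rows that start from normal. Table 4 does not give a numeric limit for Normal, and the section states no denominator for the shift tables.

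The other categorical ALT/AST summary is the PCS analysis in SAP Table 1, with a single threshold of ≥3x ULN for each enzyme. Its denominator rule is: "The percentages will be calculated based on the number of subjects with non-PCS baseline value and have at least 1 postbaseline assessment". The section adds: "All PCS values including baseline PCS values will be included in supportive listings".

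SAP 3.1 defines baseline as the last non-missing value before the first ALKS 3831 dose in A306. Under Protocol Table 3, no laboratory sample is taken at Visit 1, and footnote b makes the A305 Visit 6 assessments the baseline.

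**The concern.** Evaluating long-term safety and tolerability is the sole objective of this study, and Table 4 is the only planned table that separates a 3x ULN rise from a 5x or 10x ULN rise. Because every row requires a normal starting value, a large rise from a mildly raised baseline is not tabulated at its grade. A reader who takes the ≥5x and ≥10x rows as the number of subjects reaching those levels would undercount.

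Raised baselines are plausible here. Baseline follows four weeks of A305 treatment, with olanzapine or ALKS 3831 in two of the three sequences (SAP 3.1), and the A306 exclusion criteria (Protocol 7.2) set no explicit transaminase limit. Safety results are shown by sequence, so the restriction could remove different proportions from different columns.

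**Working it through.** The plan gives no figure to reproduce. The check applies its counting rules to example subjects and then sizes the omission under stated assumptions.

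**Counting rules.** Let b be the baseline and m the highest postbaseline value, both in multiples of ULN.
- Table 4, row k (k = 3, 5, 10): counted if b ≤ 1 and m ≥ k. Reading Normal as ≤ULN is an assumption.
- PCS percentage: counted if b < 3 and m ≥ 3. SAP 3.9.2 states the denominator only. I take the numerator to match it, as SAP 3.9.3.1 and 3.9.3.3 state for vital signs and ECG.

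| b | m | Table 4 rows | PCS ≥3x | Levels actually reached |
|---|---|---|---|---|
| 0.8 | 6 | ≥3x, ≥5x | yes | ≥3x, ≥5x |
| 0.8 | 12 | ≥3x, ≥5x, ≥10x | yes | ≥3x, ≥5x, ≥10x |
| 1.5 or 2.9 | 6 | none | yes, ungraded | ≥3x, ≥5x |
| 1.5 or 2.9 | 12 | none | yes, ungraded | ≥3x, ≥5x, ≥10x |
| 3.5 | 6 | none | no | ≥3x, ≥5x |
| 3.5 | 12 | none | no | ≥3x, ≥5x, ≥10x |

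The ≥3x row has the same restriction, but the PCS table covers it for baselines below 3x ULN. The uncovered part is the ≥5x and ≥10x grading, together with subjects at or above 3x ULN at baseline.

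**Comparison within the SAP.** In Tables 2 and 3, total cholesterol, LDL, triglycerides and glucose each have rows from an intermediate baseline and pooled rows. HDL and HbA1c do not, and neither does Table 4.

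**Size.** N = 390 is the planned enrolment (SAP section 2). The rest are assumptions: p is the share with raised baseline, r the risk of reaching ≥5x ULN from normal, and k the risk ratio for a raised baseline.
- Counted = N(1 − p)r; missed = N·p·k·r; share missed = pk/(pk + 1 − p).
- p = 10%, k = 2, r = 1%: counted 351 × 0.01 = 3.51; missed 39 × 0.02 = 0.78; share 0.78/4.29 = 18%.
- p = 15%, k = 3, r = 1%: counted 331.5 × 0.01 = 3.32; missed 58.5 × 0.03 = 1.76; share 1.755/5.07 = 35%.
- p = 20%, k = 4, r = 1%: counted 312 × 0.01 = 3.12; missed 78 × 0.04 = 3.12; share 3.12/6.24 = 50%.
- With no excess risk (k = 1), the share missed is p itself, and 0.39 to 0.78 subjects are missed over p = 10–20%.

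The share does not depend on r, but the counts scale directly with it.

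**The case against.** Much of the information survives elsewhere. A subject going from 1.5x to 12x ULN is counted in the PCS table, which also uses unscheduled values, and the value itself is listed. By-visit chemistry summaries include the maximum, so an extreme value at a scheduled visit would normally be visible. Out-of-range values judged clinically significant become adverse events (Protocol 13.1), and these are tabulated by severity. Shifts from normal are a common convention, used in this SAP for HDL and HbA1c too. The study is descriptive, and on the assumptions above the omission is a handful of subjects at most.

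All of that stands, and it limits the weight of the point. It does not remove it. The PCS row does not distinguish 12x from 3.1x ULN, a maximum is not a count, listings give no incidence, and adverse event severity (Protocol 13.4) grades functional impact and not ULN multiples.

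Four stronger readings are tempting, and the documents do not support them.
- A reader might infer that the severity of these rises disappears from the report. It does not, because the values are listed.
- A reader might infer that subjects with raised baselines are the ones most likely to reach ≥5x ULN. Neither document says so; the risk ratio in the sizing is an assumption.
- A reader might infer that rises caused by drug in A305 are already in the baseline. Prior exposure makes this possible but does not show that it happened. Protocol 5.2.1 reports no laboratory trends for samidorphan, and the first exclusion criterion in Protocol 7.2 lets the investigator or medical monitor exclude any finding that would compromise safety.
- A reader might take the PCS denominator rule as a second instance of the defect. For baselines above ULN and below 3x ULN it is a partial safeguard. Only baselines at or above 3x ULN fall outside it.

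**Conclusion.** The point holds as a limited gap in tabulation. Subjects with baseline >1 to <3x ULN who reach ≥5x or ≥10x ULN are absent from the only table that grades severity, though they remain in the PCS ≥3x ULN count and in the listings. Subjects with baseline ≥3x ULN are in neither percentage and appear only in listings.

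The structural finding follows from the SAP text, given the reading of Normal as ≤ULN and a PCS numerator that matches its denominator. The size does not follow from the text. About 0.8 to 3 missed subjects of 390 at ≥5x ULN rests wholly on the assumed 10–20% raised, 2–4 times the risk and 1% risk from normal. This is a minor improvement, worth making because safety is the sole objective and severe rises are expected to be few, so one or two uncounted subjects would be noticeable.

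**What to change.** In SAP Table 4:
- Keep the existing rows that start from Normal, and define Normal as ≤ULN.
- For ALT and AST, add ≥5x and ≥10x ULN rows for baseline >ULN to <3x ULN, and again for any baseline.
- State the denominator of each row: subjects in that baseline category with at least one postbaseline value.
- Add a bilirubin ≥2x ULN row for raised baseline in the same way.

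These rows are preferable to defining each row by a baseline below its own threshold. That rule would count a move from 4.9x to 5.1x ULN as a new ≥5x shift, and its ≥3x row would duplicate the PCS row.

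The cost is SAP and table-shell wording, since the data are already collected. There is a small downside: a few more rows with differing denominators, and an any-baseline row that will include some subjects already high at baseline. A footnote can say so.

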3.9.3. Vital Signs, Body Weight, and ECG

3.9.3.1. Vital Signs

Descriptive statistics for vital signs and changes from baseline values at each scheduled time point will be presented by treatment sequence for the treatment period.

Vital sign values will be considered PCS if they meet both the observed-value criteria and the change-from-baseline criteria listed in Table 5. The number and percentage of subjects with PCS postbaseline values will be tabulated by treatment sequence. The percentages will be calculated based on the number of subjects with non-PCS baseline values and at least 1 postbaseline assessment. The numerator will be the number of subjects with non-PCS baseline values and at least 1 postbaseline PCS value. A supportive listing of subjects with PCS postbaseline values will be provided.

All vital signs will be presented in the subject data listing.

Orthostatic hypotension (20/10 mmHg) is defined as a fall in systolic blood pressure of at least 20 mmHg and a fall in the diastolic blood pressure of at least 10 mmHg upon standing from supine. Orthostatic hypotension (30 mmHg) is defined as a fall in systolic blood pressure of at least 30 mmHg upon standing from supine.

Orthostatic tachycardia is defined as a heart rate increase of 30 beats per minute (bpm) or more upon standing from supine, or over 120 bpm upon standing.

The number and percentage of subjects with orthostatic hypotension or orthostatic tachycardia occurring at any postbaseline visit will be summarized for by treatment sequence.

Table 5: Criteria for Potentially Clinically Significant (PCS) Blood Pressure or Pulse Rate

Parameter	Criteria
Supine Systolic Blood Pressure	≤ 90 and decrease ≥ 20 mm Hg ≥ 180 and increase ≥ 20 mm Hg
Supine Diastolic Blood Pressure	≤ 50 and decrease ≥ 15 mm Hg ≥ 105 and increase ≥ 15 mm Hg
Supine Heart Rate	≤ 50 and decrease ≥ 15 bpm ≥ 120 and increase ≥ 15 bpm

3.9.3.2. Weight and Body Mass Index

Weight (kg), BMI (kg/m^2) and waist circumferences (cm) (baseline and change from baseline) will be summarized using both observed data and LOCF imputation for missing data. Absolute

and percent change from baseline in body weight will be summarized by treatment sequence and overall.

Number and percentage of subjects with $\geq 7\%$ or $\geq 10\%$ weight gain from baseline based on the observed data and LOCF will be summarized by treatment sequence and overall and by visit.

Subgroup analysis by region (US vs non-US) will be performed.

In addition, number and percentage of subjects with weight change values considered as PCS occurring at any post-baseline visit will be summarized by treatment sequence and overall. Criteria for PCS are presented below. The percentages will be calculated relative to the number of subjects in the Safety Population with at least one post-baseline value. A supportive listing will be provided for subjects with PCS values.

Table 6: Criteria for Potentially Clinically Significant (PCS) Changes from Baseline in Body Weight

Parameter	Criteria
Body Weight	Decrease from Baseline $\geq 7\%$ Increase from Baseline $\geq 7\%$

3.9.3.3. Electrocardiograms

Descriptive statistics for ECG parameters (heart rate, PR interval, RR interval, QRS interval, QT interval, and QTc interval) at baseline and change from baseline values at each scheduled assessment timepoint and at the end of the treatment period will be presented by treatment sequence for the treatment period. QTc interval will be calculated using both Bazett ($QTcB = QT/(RR)^{1/2}$) and Fridericia ($QTcF = QT/(RR)^{1/3}$) corrections; if RR is not available, it will be replaced with 60/HR in the correction formula.

Electrocardiogram parameter values are considered PCS if they meet or exceed the higher-limit PCS criteria listed in Table 7. The number and percentage of subjects with PCS postbaseline ECG values will be tabulated by treatment sequence. The percentages will be calculated based on the number of subjects with non-PCS baseline values and at least 1 postbaseline assessment. The numerator is the number of subjects with non-PCS baseline values and at least 1 postbaseline PCS value. A supportive listing of subjects with PCS values will be provided.

Table 7: Criteria for Potentially Clinically Significant (PCS) QTcB and QTcF

Parameter	Criteria
QTcB and QTcF	>450 to ≤ 480 msec
	>480 to ≤ 500 msec
	>500 msec
	Change from baseline >30 to ≤ 60 msec

Parameter	Criteria
	Change from baseline >60 msec

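### The QTc outlier table limits every row to subjects with a non-PCS baseline; read literally, anyone above 450 msec at baseline drops out of all rows

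*SAP*

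**What the plan says.** SAP 3.9.3.3 defines the status of a value: "Electrocardiogram parameter values are considered PCS if they meet or exceed the higher-limit PCS criteria listed in Table 7". Table 7 then gives five rows for QTcB and QTcF. Three are absolute: ">450 to ≤ 480 msec", ">480 to ≤ 500 msec", and above 500 msec. Two are changes: "Change from baseline >30 to ≤ 60 msec" and "Change from baseline >60 msec".

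Baseline status limits both parts of the percentage. For the denominator: "The percentages will be calculated based on the number of subjects with non-PCS baseline values and at least 1 postbaseline assessment". For the numerator: "The numerator is the number of subjects with non-PCS baseline values and at least 1 postbaseline PCS value". The section does not say whether non-PCS means outside every row of Table 7 or outside the row being tabulated. It also does not say whether a subject is classified on the worst postbaseline value. It does add: "A supportive listing of subjects with PCS values will be provided".

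Protocol 14.4 plans the number and percentage of subjects meeting PCS criteria at any post-Baseline visit, ECG included, and states no baseline restriction. SAP section 5 declares no major deviation from the protocol's analysis.

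**The concern.** A restriction to non-PCS baselines suits a single cut-off, where it isolates newly emergent abnormality. Table 7 is not a single cut-off. It grades severity in closed bands and adds two change criteria. One baseline exclusion applied across all of them can remove a subject from the >500 msec row because of a baseline just over 450 msec.

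Long-term safety and tolerability is the study's only objective, and this table gives the headline incidence of QTc outliers. The choice of baseline adds to the concern. SAP 3.1 uses the last value before the first ALKS 3831 dose in this study, and Protocol Table 3 takes it from the final treatment visit of ALK3831-A305. Subjects in two of the three treatment sequences have by then had four weeks of olanzapine or ALKS 3831. A QTc that passed 450 msec during that time would take the subject out of this study's table, so the exclusion could differ between the sequences being tabulated.

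**Working it through.** The plan states no figure to reproduce, and the study has no formal sample size calculation. The check is on the counting rule.

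**Three readings**

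- *Any-row:* a baseline value meeting any Table 7 criterion, meaning above 450 msec, is PCS. The subject leaves the numerator and denominator of all rows.
- *Band-by-band:* baseline status is judged separately for each band.
- *Cumulative:* each absolute row is a lower threshold (>450, >480, >500 msec), and the subject must be at or below that threshold at baseline.

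**Worked cases** (the cumulative column covers absolute rows only)

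| Baseline → postbaseline, msec | Change | Any-row | Band-by-band | Cumulative |
|---|---|---|---|---|
| 440 → 510 | +70 | >500; change >60 | >500; change >60 | >450, >480, >500 |
| 455 → 510 | +55 | no row | >500; change >30 to ≤60 | >480, >500 |
| 455 → 520 | +65 | no row | >500; change >60 | >480, >500 |
| 490 → 510 | +20 | no row | >500 | >500 |
| 490 → 470 | −20 | no row | >450 to ≤480 | none |

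**All transitions.** The four QTc categories (≤450, >450 to ≤480, >480 to ≤500, >500) were represented by 440, 465, 490 and 520 msec. That gives 4 × 3 / 2 = 6 worsening and 6 improving moves.

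- Any-row misses 3 of 6 worsenings: 465→490, 465→520 and 490→520.
- Band-by-band counts 3 of 6 improvements as cases in a lower band: 490→465, 520→465 and 520→490.
- Cumulative misses 0 of 6 worsenings and counts 0 of 6 improvements.

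**Change rows.** Change from baseline is zero at baseline, so row by row nobody is PCS and the restriction excludes no one. These rows lose subjects only under the any-row reading.

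**Comparison with the SAP's other PCS rules**

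- Laboratory criteria (3.9.2) are mostly simple cut-offs, where the restriction works.
- Vital signs (3.9.3.1) need a value and a change together. A baseline value cannot meet both, so the same sentence excludes no one.
- Weight (3.9.3.2) is a pure change criterion. It uses all Safety Population subjects with a postbaseline value and has no baseline restriction.

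Among these rules, only the ECG section joins the restriction to graded bands.

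**Size, as illustration only.** The documents give no QTc distribution. The assumptions are:

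- 390 subjects, normal baseline QTc, and the five scheduled postbaseline ECGs (Weeks 4, 12, 24, 36 and 52);
- each postbaseline value = mean + 0.7 × (baseline − mean) + normal error with SD 12;
- no drug effect and no dropout.

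A new >480 case has baseline ≤480 and a worst postbaseline value >480. The table gives expected numbers of subjects.

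| Assumed mean, SD (msec) | Baseline >450 | New >480: all / kept under any-row | Baseline >480 entering the lowest band under band-by-band |
|---|---|---|---|
| 405, 18 | 2.4 (0.6%) | 0.01 / 0.00 | 0.01 |
| 410, 20 | 8.9 (2.3%) | 0.10 / 0.01 | 0.10 |
| 420, 22 | 33.7 (8.6%) | 1.09 / 0.05 | 1.24 |
| 430, 25 | 82.5 (21.2%) | 6.04 / 0.16 | 8.80 |

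The effect runs from negligible to several subjects, depending entirely on the assumed distribution.

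**The case against.** The strongest reply is that the wording allowing a value to meet or exceed a criterion makes each row a lower threshold. On that view 490 msec already exceeds the first row, so 490→470 is not a new case, and 455→510 counts above 500. Both errors vanish. This stands as a possible reading, so it would be wrong to infer that every reading miscounts. But two of the absolute rows and one change row carry printed upper limits, which a cumulative reading would have to ignore.

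It can also be said that the band-by-band reading is the one the text supports least, because status is defined for the value and 490 msec meets a row. That is fair, and it makes the any-row reading the more literal one.

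A reader might infer that serious cases are hidden. The documents do not support this. The ECG listing covers subjects with PCS values and is not confined to postbaseline values, all source data are listed, and by-visit summaries include the maximum. One qualification applies: SAP section 7 keeps unscheduled measurements out of by-visit summaries, so an unscheduled 510 msec in an excluded subject would appear only in listings.

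Restricting to newly emergent abnormality is a legitimate convention, used elsewhere in this SAP. Table shells and programming specifications are separate documents and may settle the reading, but the SAP should not depend on them. Finally, the table is descriptive, and no test or stopping rule in either document uses it.

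**Conclusion.** The point holds in limited form. On its most literal reading, SAP 3.9.3.3 removes every subject with baseline QTc above 450 msec from all rows of the outlier table, including the >500 msec and change rows. Band-by-band, it counts some improvements as cases. The one reading free of both faults conflicts with Table 7 as printed.

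The rule is also narrower than Protocol 14.4. A reader might call that an undeclared protocol breach. The documents do not go that far: Protocol 14.2 leaves further detail to the SAP, and SAP section 5 speaks only of major deviations.

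A reader might also put a large share on the loss. For example, if 10% of 390 subjects (39) had baseline above 450 msec, with a 3% risk of exceeding 500 msec against 0.3% in the other 351, the any-row reading would drop 0.03 × 39 = 1.17 of 1.17 + 0.003 × 351 = 2.22 expected cases, or 53%. With 5% or 15% above 450 msec the share is 34% or 64%. All these rates are assumed, none is in the documents, and the 53% concerns about two expected cases. The size is therefore unknown.

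The counting fault itself needs no rates. Severity is minor to moderate: one descriptive safety percentage is affected, not the visibility of the subjects.

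**What to change.** In SAP 3.9.3.3 and Table 7:

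- **Absolute rows:** replace the bands with cumulative thresholds (>450, >480, >500 msec), with each subject classified on the worst postbaseline value. The denominator for each row is subjects at or below that row's threshold at baseline with at least one postbaseline ECG. A baseline-by-worst-postbaseline shift table would serve equally well.
- **Change rows:** use increases of >30 and >60 msec, with all subjects who have a baseline and at least one postbaseline ECG as the denominator. This follows what the SAP already does for weight change.
- **Protocol link:** state in SAP section 5 how these denominators relate to Protocol 14.4.

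The cost is SAP and table-shell wording. No new data are needed, and nothing in the conduct of the study changes.
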